8.7.4. Adjusted comparison of OS between treatment groups

Finally, an adjusted comparison of OS across treatment groups (i.e., ENCO+BINI [pooled across COLUMBUS and Flatiron EHR], DAB+TRAM and VEM+COBI) will be conducted. Hazard ratios will be estimated based on a multivariable Cox proportional hazard model, adjusting for key baseline characteristics known or expected to be related to OS in metastatic melanoma (e.g., age, sex, race, BMI, ECOG, LDH, time from initial melanoma diagnosis to metastatic disease, time from metastatic diagnosis to treatment initiation, treatment experience in the therapeutic setting, prior IO/chemotherapy in the adjuvant setting, prior surgery in the adjuvant setting). Specific adjustment factors listed here may be revised based on expert clinical input.

The adjusted analyses will be conducted in each of the datasets with imputed baseline characteristic values in turn. Log-hazard ratios for OS comparing treatment with ENCO+BINI relative to DAB+TRAM and VEM+COBI each imputed dataset will be obtained, and summary HRs obtained by pooling results across all imputed datasets will be generated using Rubin's rules. ¹⁶

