8.2.1.2. Flatiron Health data

Pfizer has contracted with Flatiron for a custom data extract containing information on patients with advanced melanoma. Eligibility criteria applied to the Flatiron custom data received by Pfizer include:

- Diagnosed with melanoma based on International Classification of Disease 9th and 10th Revisions (ICD-9: 172.x; ICD-10: C43x, D03x) and ≥2 visits on different days in the Flatiron database on or after January 1, 2011.
- Clinically confirmed diagnosis of melanoma with pathologic stages III or IV at initial diagnosis or earlier stage disease with a first locoregional or distant recurrence on or after January 1, 2011.
- Age ≥18 years at the time of advanced melanoma diagnosis.
- Evidence of ≥1 BRAF positive test result at any time based on laboratory or genetic analysis results.
- Treatment with ≥1 BRAF-inhibitor (i.e., encorafenib, dabrafenib, vemurafenib) and treatment with ≥1 MEK-inhibitor (i.e., binimetinib, trametinib, cobimetinib) in 1L or 2L line of therapy (LOT), as defined per Flatiron's LOT business rules.

 Earliest LOT containing a BRAF- and MEK-inhibitor ≥3 months prior to data cutoff (defined as 30 September 2021)

Key inclusion criteria from the COLUMBUS trial will be applied to the Flatiron RWD population to align the populations to the extent possible between the CTD and RWD sources. The sample of patients from the Flatiron Health EHR data for this study will be identified using the following additional criteria applied to the custom data cut received from Flatiron:

- At least 18 years of age at the index date
- Confirmed BRAF V600E or V600K activating mutation reported in the data based on laboratory or genetic analysis results
- Treatment-naive or had previous 1L IO at index date in the therapeutic setting, based on review of medication orders or administration prior to the index date.
- ECOG status of 0 or 1 at the index date

The following criteria will be additionally used to identify patients receiving each of the treatments of interest:

- ENCO+BINI treatment group: At least 1 order or administration of ENCO+BINI treatment after the diagnosis of metastatic melanoma and after 27 June 2018 (FDA approval date for ENCO+BINI for use in patients with metastatic melanoma).
- DAB+TRAM treatment group: At least 1 order or administration of DAB+TRAM treatment after the diagnosis of metastatic melanoma and after 09 January 2014 (FDA approval date for DAB+TRAM for use in patients with metastatic melanoma).

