Body mass index (BMI) at index	Baseline Characteristic / Potential Confounder	COLUMBUS trial data; Flatiron EHR	Defined as weight (in kg) divided by squared height (in m²)
ECOG at index	Baseline Characteristic / Potential Confounder	COLUMBUS trial data; Flatiron EHR	0, 1, Unknown/Missing; defined during the baseline period of both the COLUMBUS trial data and Flatiron EHR
BRAF mutation status	Baseline Characteristic / Potential Confounder	COLUMBUS trial data; Flatiron EHR	V600E, V600K, Unknown/Missing
AJCC disease stage at initial melanoma diagnosis	Baseline Characteristic / Potential Confounder	COLUMBUS trial data; Flatiron EHR	0, I, II, III, IV, or Unknown/Missing; defined at initial melanoma diagnosis for COLUMBUS trial data and Flatiron EHR
AJCC disease stage at treatment initiation	Baseline Characteristic	COLUMBUS trial data	IIIB, IIIC, IVM1a, IVM1b, or IVM1c; defined at treatment initiation in the COLUMBUS trial data. Not available in the Flatiron EHR
Lactate dehydrogenase (LDH) at index	Baseline Characteristic / Potential Confounder	COLUMBUS trial data; Flatiron EHR	Evaluated in units per liter (U/L) and defined at trial baseline in COLUMBUS trial and during the baseline period in Flatiron EHR
Time from initial melanoma diagnosis to metastatic disease	Baseline Characteristic / Potential Confounder	COLUMBUS trial data; Flatiron EHR	Duration (in months) from melanoma diagnosis to the development of metastatic disease
Time from metastatic melanoma diagnosis to treatment initiation	Baseline Characteristic / Potential Confounder	COLUMBUS trial data; Flatiron EHR	Duration (in months) from metastatic melanoma diagnosis to the initiation of treatment
Year of treatment initiation	Baseline Characteristic	COLUMBUS trial data; Flatiron EHR	Calendar year when treatment was initiated
Region	Baseline Characteristic	COLUMBUS trial data; Flatiron EHR	Europe, North America, Australia, Other, or Missing
Treatment experience in the therapeutic setting	Baseline Characteristic / Potential Confounder	COLUMBUS trial data; Flatiron EHR	Indicates whether patients received targeted therapy as first-line treatment (e.g., Treatment naïve) or as second- line treatment after a prior line of immunotherapy treatment (e.g., Prior 1L IO therapy)

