Prior systemic therapies in the adjuvant setting	Baseline Characteristic /Potential Confounder	COLUMBUS trial data; Flatiron EHR	Indicates whether patients previously received systemic therapy (e.g., prior surgery, radiotherapy, immunotherapy, or chemotherapy) before initiating treatment
Prior surgery in the adjuvant setting	Baseline Characteristic / Potential Confounder	COLUMBUS trial data; Flatiron EHR	Indicates whether patients previously used surgery to reduce/remove tumors as a form of treatment
Prior radiotherapy in the adjuvant setting	Baseline Characteristic / Potential Confounder	COLUMBUS trial data; Flatiron EHR	Indicates whether patients underwent radiotherapy among those receiving prior systemic therapy

Prior IO or chemotherapy in the adjuvant setting	Baseline Characteristic / Potential Confounder	COLUMBUS trial data; Flatiron EHR	Indicates whether patients underwent chemotherapy or immunotherapy among those receiving prior systemic therapy
Number of LOTs after TT treatment initiation	Baseline Characteristic / Potential Confounder	COLUMBUS trial data; Flatiron EHR	Indicates the number of LOTs occurring after treatment initiation $(0, 1, \ge 2$, or Missing)
Number of organs involved	Baseline Characteristic	COLUMBUS trial data; Flatiron EHR	Indicates number of organs involved or sites of metastases at baseline (1, 2, or ≥3), with all patients having at least 1 site given diagnosis of metastatic disease. This data was collected and reported in COLUMBUS. In Flatiron EHR, it will be derived based on counting the number of distinct sites recorded as having metastases based on ICD codes.
Presence of lung metastases	Baseline Characteristic	COLUMBUS trial data; Flatiron EHR	Indicates whether patients had lung metastases. This data was collected and reported in COLUMBUS. In Flatiron EHR, it will be derived based on having ICD codes reflecting presence of lung or respiratory organ metastases (ICD-9: 197, 197.1; ICD-10: C78.01, C78.02, C78.1, C78.2, C78.30, C78.39).
Presence of liver metastases	Baseline Characteristic	COLUMBUS trial data; Flatiron EHR	Indicates whether patients had liver metastases. This data was collected and reported in COLUMBUS. In Flatiron EHR, it will be derived based on having ICD codes reflecting presence of liver metastases (ICD-9: 197.7; ICD-10: C78.7)

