8.4. Data sources

COLUMBUS trial

COLUMBUS was a two-part, multicenter, randomized, open-label, Phase 3 clinical trial. ¹⁰ Part 1 of the trial investigated the effectiveness and safety of three treatment regimens in patients with locally advanced unresectable or metastatic BRAFV600-mutant metastatic melanoma who were treatment naïve or whose cancer had progressed after 1L IO. In Part 1 of the trial, patients were randomized to one of three treatment arms: 1) 450mg once daily encorafenib and 45mg twice daily binimetinib (n=192), 2) 960mg twice daily vemurafenib (n=191) and 3) 300mg once daily

encorafenib (n=194). Randomization was stratified by AJCC disease stage (IIIB, IIIC, IVM1a, IVM1b, or IVM1c), ECOG performance status (0, 1), and BRAFV600 mutation profile (V600E, V600K). Progression-free survival was the primary endpoint in the trial, while OS was one of the secondary endpoints. Patients were enrolled in Part 1 of the trial between 30 December 2013 through 10 April 2015.

The ENCO+BINI arm of Part 1 of the trial will be used in this study (database lock date: 15 September 2020). Part 2 of the trial compared encorafenib 300mg once daily plus binimetinib 45mg twice daily versus encorafenib 300mg once daily alone and will not be considered.

Flatiron Health EHR

The Flatiron Health EHR database is a longitudinal, de-identified real-world database derived from EHRs collected in US cancer clinics. The database covers more than 2.6 million active cancer patients treated at over 800 sites of care across 4 US census regions. Patient-level data includes both structured (diagnosis, demographics, laboratory values, biomarker information, drug orders, visits, etc.) and unstructured (physician notes, radiology, and pathology reports, etc.) sources. Data on death is drawn from structured or unstructured data fields in the EHR, and publicly available sources of mortality including the US Social Security Death Index, and commercial obituary data. ¹³

Pfizer has contracted with Flatiron for a custom data extract containing information on patients with advanced melanoma who received treatment with BRAF- or MEK-inhibitor therapies. Patients meeting the eligibility criteria defined for this study will be obtained from this custom data extract as described in Section 8.2 and used in all analyses.

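### BRAF subtype, initial AJCC stage and prior radiotherapy are labelled potential confounders but are absent, without a stated reason, from the listed adjustment set for the primary OS model

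*Protocol*

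**What the plan says.** Protocol 8.7.4 lists, as examples, "age, sex, race, BMI, ECOG, LDH, time from initial melanoma diagnosis to metastatic disease, time from metastatic diagnosis to treatment initiation", followed by "treatment experience in the therapeutic setting, prior IO/chemotherapy in the adjuvant setting, prior surgery in the adjuvant setting". That makes 11 factors. It adds: "Specific adjustment factors listed here may be revised based on expert clinical input". SAP 7.1 and the primary-outcome row of SAP Table 3 repeat the list and the caveat. Appendix Table 3 in both documents describes its rows as the expected adjustment factors and shows the same set.

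Protocol Table 1 gives each variable a role. Three that carry the potential-confounder label, with both sources named, are not in the list:

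- BRAF mutation status, with categories "V600E, V600K, Unknown/Missing".
- "AJCC disease stage at initial melanoma diagnosis", recorded as 0 to IV or unknown/missing.
- Prior radiotherapy in the adjuvant setting, defined as "Indicates whether patients underwent radiotherapy among those receiving prior systemic therapy".

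On BRAF, the Flatiron inclusion criteria require "Confirmed BRAF V600E or V600K activating mutation reported in the data based on laboratory or genetic analysis results". COLUMBUS likewise required V600E or V600K before enrolment. Protocol 8.4 gives the COLUMBUS stratification factors as AJCC stage together with "ECOG performance status (0, 1), and BRAFV600 mutation profile (V600E, V600K".

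The limitations in protocol 8.9 explain why number and sites of metastases will not be adjusted for. They do not mention these three variables. SAP 7.1 says a sensitivity analysis with further covariates may be done, but does not name the covariates.

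**The concern.** The pooled ENCO+BINI group combines 192 randomised trial patients with Flatiron patients, and both comparators come from Flatiron alone. Beyond restriction through the eligibility criteria, covariate adjustment is what protects the comparison. The plan accepts that number and sites of metastases cannot be used, and it records stage at treatment initiation as unavailable in Flatiron. The remaining measured markers of disease and prior treatment therefore matter more.

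The potential-confounder label is selective: year of initiation, region, number of organs and the metastatic-site variables do not carry it. A reader would expect each labelled variable either to enter the model or to have a reason for staying out. If one of the three differs between groups and predicts death given the listed factors, the adjusted hazard ratios for ENCO+BINI carry a bias that data already in hand could reduce.

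**Working it through.** **Step 1. Compare the labels with the model.** The inputs are protocol Table 1, the list in 8.7.4 (matching SAP 7.1) and the Appendix Table 3 rows. Table 1 labels 16 variables as potential confounders. The model lists 11, all among the 16, which leaves 16 − 11 = 5:

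| Labelled but not listed | Observation |
|---|---|
| BRAF V600E/K subtype | Required for eligibility in both sources; COLUMBUS stratification factor; no missing row in Appendix Table 1 |
| AJCC stage at initial diagnosis | Unknown/missing allowed; already a candidate variable for MICE |
| Prior adjuvant radiotherapy | Defined only within patients who had prior systemic therapy; no row in Appendix Table 1 |
| Prior systemic therapies, adjuvant | Composite that overlaps listed items |
| Number of LOTs after TT initiation | Measured after baseline |

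The last two have an evident reason to stay out. The first three have none in the text.

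**Step 2. Feasibility of BRAF.** Of the three COLUMBUS stratification factors, ECOG is in the model and stage at initiation is unavailable in Flatiron. BRAF subtype is available in both sources but unlisted. It is binary, so it costs one degree of freedom. Table 1 still allows an unknown category, which does not fit the eligibility rule and should be reconciled.

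**Step 3. Illustrative size.** The plan states no figure to reproduce, and gives no prevalences, factor effects or event counts. Every input here is an assumption. For one omitted binary factor with hazard ratio HRc for death, prevalence p1 in ENCO+BINI and p0 in the comparator, the Bross factor on the ENCO+BINI versus comparator hazard ratio is

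[1 + p1(HRc − 1)] / [1 + p0(HRc − 1)].

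| HRc | p1, p0 | Calculation | Factor | Groups swapped |
|---|---|---|---|---|
| any | equal | – | 1.00 | 1.00 |
| 1.2 | 0.10, 0.15 | 1.020/1.030 | 0.99 | 1.01 |
| 1.3 | 0.25, 0.35 | 1.075/1.105 | 0.97 | 1.03 |
| 1.5 | 0.10, 0.20 | 1.050/1.100 | 0.95 | 1.05 |
| 1.5 | 0.25, 0.45 | 1.125/1.225 | 0.92 | 1.09 |
| 2.0 | 0.10, 0.30 | 1.100/1.300 | 0.85 | 1.18 |

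For HRc 1.2 to 1.5 and imbalances of 5 to 20 points, the shift is about 1% to 9% per factor, with a sign set by which group has the higher prevalence. The last row is a more extreme assumption, shown for range. The formula treats the factor as unrelated to the 11 listed ones. Correlation with them would normally reduce what remains, and several omitted factors may add up or cancel.

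**The case against.** **The list is open.** It is introduced by way of example, may be revised on clinical input, and the SAP allows extra covariates. This stands against saying that the three variables have been finally excluded. It does not answer the point: the same 11 factors recur as the expected set in both documents, the extra analysis is optional, and nothing commits the sponsor to any of the three.

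**The label is not decisive.** Number of LOTs after TT initiation carries it too, and a post-baseline variable should not be adjusted for. This stands. The label marks candidates, so each needs its own argument. BRAF has one that does not rest on the label: eligibility, stratification and near-complete recording.

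**Clinical input shaped the list.** The summary of changes says that adjustment factors were updated after discussion with a melanoma expert. That is a process, not a reason for these variables, and a sentence on each would settle it.

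**Stage and radiotherapy are weaker cases.** Stage IV at diagnosis implies a time from initial diagnosis to metastatic disease near zero, so stage overlaps with a listed factor. COLUMBUS stratified on stage at enrolment, which is a different variable. Radiotherapy, as defined, has no stated value for patients without prior systemic therapy and cannot enter a whole-cohort model. Both objections stand and limit what can be asked.

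**Stronger readings.** A reader might infer that the hazard ratios will be confounded by these omissions. The documents show neither imbalance between groups nor an effect on OS beyond the 11 factors. A reader might also infer that BRAF subtype is known for everyone and needs no imputation. Eligibility points that way, but the unknown category in Table 1 means it is not assured.

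**Conclusion.** The plan does not reconcile its own potential-confounder labels with its listed adjustment set, and three variables available in both sources are left outside it without explanation. Potentially avoidable confounding may remain. Whether it does, how large it is and which group it favours cannot be determined from the documents. The range of about 1% to 9% per factor rests wholly on assumed effects and prevalences, and the true value is zero under balance.

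The case is firm for BRAF subtype and moderate for initial stage. For radiotherapy it depends on a new definition. The documents do not support requiring all three in the primary model, or adding every variable that carries the label.

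**What to change.** 1. **BRAF.** In protocol 8.7.4, SAP 7.1, SAP Table 3 and the Appendix Table 3 shell, add V600K versus V600E to the primary adjusted Cox model, and include it in the MICE models. Reconcile the unknown category in Table 1 with the eligibility requirement.
2. **Initial stage.** Make the additional-covariate sensitivity analysis mandatory and name its covariates. Include AJCC stage at initial diagnosis (for example 0–II, III, IV), with unknown values imputed. It may go into the primary model instead if its overlap with time from initial diagnosis to metastatic disease is judged acceptable.
3. **Radiotherapy.** Redefine it as yes/no for all patients, then include it in that sensitivity analysis.
4. **Number of LOTs after TT initiation.** Leave it out and correct its label, since it is post-baseline.

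The cost is wording plus a few model degrees of freedom: one for BRAF, two for stage in three groups and one for radiotherapy, four at most. All are variables the plan already intends to derive; radiotherapy needs recoding.

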8.7.5. Exploratory analyses of PFS

Analyses assessing PFS will also be explored. PFS will be defined as described in Section 8.3. PFS will be summarized for all treatment groups.

Suitability of comparative analyses of PFS between treatment groups will be determined following additional data exploration to characterize number and frequency of assessments of PFS available in these settings, and discussion of comparability of the assessment of disease progression in RWD vs CTD. If analyses of PFS are deemed suitable based on these evaluations,

unadjusted and adjusted comparisons of PFS will be conducted using the methods described in Sections 8.7.2 and 8.7.4.

8.8. Quality control

Best practice guidelines will be followed to ensure project quality, including structured organization of project materials (e.g., data extracts, statistical software programs, output tables) and standard internal audit process. The audit process both confirms the validity of the analytical approach and ensures that all programs and results are accurate.

8.9. Strengths and limitations of the research methods

The strengths of this study include:

- Key inclusion criteria with respect to diagnosis, disease stage, age, BRAFV600 mutation and ECOG status in the COLUMBUS trial will be applied to the Flatiron RWD to the extent possible to obtain a comparable group of patients across both settings
- Adjustment will be made for multiple baseline characteristics to mitigate bias due to potential differences in these characteristics across the treatment groups
- Concerns about differences in outcome assessment across trial and RWD settings are
 mitigated for OS given the availability of a real-world mortality endpoint in the Flatiron
 RWD that has high sensitivity, specificity, positive predictive values, negative predictive
 values and agreement when compared against the National Death Index (NDI), the goldstandard source for mortality data in the US.¹⁷

The limitations of this study include the following:

- Application of the COLUMBUS trial inclusion criterion requiring at least 1 measurable lesion based on Response Evaluation Criteria in Solid Tumors (RECIST) version 1.1 criteria will not be implemented due to absence in Flatiron EHR of systematic radiographic imaging to assess tumor response as required by RECIST.
- While adjustment will be made for available baseline characteristics across treatment
 groups, differences due to factors that were not adjusted for may still contribute to
 observed differences in OS between settings. For instance, data on number and sites of
 metastases, while systematically collected in the COLUMBUS trial, can only be derived
 based on ICD codes in Flatiron EHR. Based on clinical input, data on number and sites
 of metastases will very likely be underestimated in the Flatiron EHR, and not
 comparable to the corresponding data from COLUMBUS, precluding adjustment for
 these variables.

- The analysis conducted here is analogous to an 'intent-to-treat' perspective, and therefore will not account for potential differences in adherence and post-baseline treatments between trial and real-world settings.
- The COLUMBUS trial was a multi-national trial that recruited patients from 160+ sites in 28 countries, and therefore covers a broader range of geographies than the US-based Flatiron RWD; differences in background care across geographies and care settings may contribute to differences in outcomes between the CTD and RWD.

8.10. Other aspects

Not applicable.

9. PROTECTION OF HUMAN SUBJECTS

9.1. Patient information

This study involves data that exist in anonymized structured format and contain no patient personal information.

9.2. Patient consent

As this study involves anonymized structured data, which according to applicable legal requirements do not contain data subject to privacy laws, obtaining informed consent from patients by Pfizer is not required.

9.3. Institutional review board (IRB)/Independent ethics committee (IEC)

This retrospective database analysis does not involve the collection, use, or transmittal of individually identifiable data. As such, the study falls within the definition of exempt research under 45 CFR 46.104(d)(4)(ii) and IRB approval is not required. Because the dataset does not include individually identifiable health information under 45 CFR 164.514, Health Insurance Portability and Accountability Act (HIPAA) requirements do not apply.

